7.1.4. Serious

An adverse event or suspected adverse reaction is considered serious if in the view of the investigator or the sponsor, it results in any of the following:

- Death,

- A life-threatening adverse drug experience
- Inpatient hospitalization or prolongation of existing hospitalization
- Persistent or significant incapacity or substantial disruption of the ability to conduct normal life functions
- A congenital anomaly/birth defect.
- Important medical events that may not result in death, be life-threatening, or require hospitalization may be considered a serious adverse drug experience when, based upon appropriate medical judgment, they may jeopardize the patient or subject and may require medical or surgical intervention to prevent one of the outcomes listed in this definition.

7.1.5. Disability

A substantial disruption of a person's ability to conduct normal life functions.

7.1.6. Life-threatening adverse drug experience

Any adverse event or suspected adverse reaction that places the patient or subject, in the view of the investigator or sponsor, at immediate risk of death from the reaction as it occurred, i.e., it does not include a reaction that had it occurred in a more severe form, might have caused death.

7.1.7. Protocol Deviation (NIH Definition)

A protocol deviation is any change, divergence, or departure from the study design or procedures of a research protocol that is under the investigator's control and that has not been approved by the IRB.

7.1.8. Protocol Violation (NIH Definition)

Any change, divergence, or departure from the study procedures in an IRB-approved research protocol that has a major impact on the subject's rights, safety, or well-being and/or the completeness, accuracy or reliability of the study data.

7.1.9. Unanticipated Problem

Any incident, experience, or outcome that:

- Is unexpected in terms of nature, severity, or frequency in relation to
 - (a) the research risks that are described in the IRB-approved research protocol and informed consent document; Investigator's Brochure or other study documents, and
 - (b) the characteristics of the subject population being studied; AND
- Is related or possibly related to participation in the research; AND
- Places subjects or others at a greater risk of harm (including physical, psychological, economic, or social harm) than was previously known or recognized.

7.2. Routine Data Reporting

7.2.1. Following randomization, all adverse events will be described in the source documents, reviewed by the designated research nurse, and captured in C3D.

- All chemotherapy dose reductions and the reason for the reduction will be captured in C3D
- During the follow up period (more than 30 days following the last treatment), only those events that are serious, unexpected, and related to the treatment will be captured in C3D.

7.2.2. Laboratory events will be captured as follows:

- During hospitalization for surgical resection, only the admission labs, first morning labs drawn after 4am, and labs that support the diagnosis of a reportable event will be uploaded into C3D.
- During systemic chemotherapy regimen, for laboratory values obtained at sites other than the NIH Clinical Center: only the following values (highest grade per cycle) will be captured in C3D:
 - Hemoglobin, total white blood cell count, absolute neutrophil count, platelet count
 - PTT, PT or INR
 - Creatinine, ALT, AST, Bilirubin (total and direct),
 - Any unexpected laboratory abnormality \geq grade 2 possibly, probably or definitely related to the research

7.3. Exclusions to Routine Data Reporting:

The following Adverse Events will be captured only in the source documents and will not be reported in C3D

7.3.1. For the duration of the study:

- Laboratory values that do not support the diagnosis of a reportable event
- All grade 1 events

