3.1. Staging Laparoscopy

3.1.1. Patients who meet eligibility criteria will be taken to the operating room for staging laparoscopy and peritoneal washings. At laparoscopy biopsies of the peritoneum will be done and used later to confirm status of peritoneal disease (not as a part of the staging procedure but as part of the study).

- Any suspicious lesions that might preclude resection to NED will be biopsied as well.
- Liver ultrasound to confirm axial imaging findings will be done.
- Randomization and stratification will be done after laparoscopy and only after the results of the peritoneal washings are known (within one week of laparoscopy).

3.1.2. Patients will then be randomized to receive gastrectomy and/or metastasectomy plus systemic therapy (GYMS arm) or systemic therapy alone (SA arm).

- Patients randomized to receive the standard of care (SA arm) will receive systemic therapy (as described in Section 3.5). **Note:** Patients may undergo palliative gastrectomy if indicated but must begin chemotherapy within 6 weeks of gastrectomy (8 weeks following randomization).
- Patients randomized to receive gastrectomy and/or metastasectomy plus systemic therapy (GYMS arm) will be taken to the operating room within 1-2 weeks of randomization (as soon as feasible). Patients may undergo surgery only at the NCI. Subsequently, patients will receive systemic therapy within 4 to 16 weeks after surgery and/or when fully recovered from surgery. Patients who do not recover within 16 weeks will be taken off treatment and followed for survival. (**Note:** patients who undergo thoracotomy for pulmonary metastases must be able to receive systemic therapy within 24 weeks of their initial surgery.) This is an intent-to-treat phase III trial.

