6.2. Evaluation of Potential Benefits and Risks

The potential benefit to patients undergoing this therapy would be palliation in terms of preventing or delaying intra-abdominal tumor progression and metastases elsewhere which can be a devastating and painful source of symptoms and cause for demise. In addition, significant tumor response may extend progression free and overall survival. The risks for this protocol include the risks associated with any abdominal surgery. This includes postoperative bleeding, intra-abdominal infection, enterocutaneous fistulas, anesthetic mishap and perioperative death. In addition, the toxicities of chemotherapy place the patients under risk. A combination of surgery and chemotherapy may decrease healing at a time when healing of abdominal wounds and bowel anastomosis is essential for recovery. All attempts will be made to avoid enterotomies or a bowel resection where feasible. In the case of intraabdominal catastrophe after surgery, patients may require reoperation.

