7.1. DEFINITIONS

7.1.1. Adverse Event

An adverse event is defined as any reaction, side effect, or untoward event that occurs during the course of the clinical trial associated with the use of a drug in humans, whether or not the event is considered related to the treatment or clinically significant. For this study, AEs will include events reported by the patient, as well as clinically significant abnormal findings on physical examination or laboratory evaluation. A new illness, symptom, sign or clinically significant laboratory abnormality or worsening of a pre-existing condition or abnormality is considered an AE. All AEs must be recorded on the AE case report form unless otherwise noted above in Section 6.1.

All AEs, including clinically significant abnormal findings on laboratory evaluations, regardless of severity, will be followed until satisfactory resolution. AEs should be reported up to 30 days following the last dose of study drug. AEs that are considered treatment related, expected, continuing, but not resolvable by 30 days after treatment completion (e.g., alopecia) will not be followed after the 30-day period.

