7.4.2. NCI-IRB Requirements for PI Reporting of Adverse Events at Continuing Review

The protocol PI will report to the NCI-IRB:

- All Grade 2 unexpected events that are possibly, probably or definitely related to the research;
- All Grade 3 and 4 events that are possibly, probably or definitely related to the research;
- All Grade 5 events regardless of attribution;
- All Serious Events regardless of attribution.

NOTE: Grade 1 events are not required to be reported

8. Pharmaceutical Information:

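### For patients whose operation is their last treatment, 7.2.1 keeps late, expected surgical complications out of the database; capture also opens only after the study laparoscopy

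*Combined protocol and SAP*

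**What the plan says.** **When capture starts and narrows.** Section 7.2.1 opens with "Following randomization, all adverse events will be described in the source documents", followed by nurse review and entry in C3D. In the follow-up period, which it defines as beyond 30 days from the last treatment, "only those events that are serious, unexpected, and related to the treatment will be captured in C3D". Section 7.1.1 has a different clock: "AEs should be reported up to 30 days following the last dose of study drug".

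**Rules by phase.** Section 7.3 lists what stays in source documents only. Grade 1 events are excluded throughout (7.3.1). For post-operative recovery after discharge, 7.3.3 excludes grade 2 events and nothing more. It gives no end date for that phase.

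**Patients who stop after surgery.** Section 3.1.2 allows 4 to 16 weeks between surgery and chemotherapy (24 weeks with thoracotomy) and states: "Patients who do not recover within 16 weeks will be taken off treatment and followed for survival". Section 3.2.6 removes patients whose disease cannot be adequately debulked, and 3.8 lists withdrawal, progression and physician judgement as further reasons to stop.

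**Which harms are foreseen.** On the risks of abdominal surgery, 6.2 says: "This includes postoperative bleeding, intra-abdominal infection, enterocutaneous fistulas, anesthetic mishap and perioperative death".

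**What the safety reviews use.** The DSMB comparison in 5.4 covers toxicities at least possibly attributed to the arm's therapy. At continuing review, 7.4.2 requires "All Serious Events regardless of attribution".

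**Laparoscopy.** It precedes randomization. Section 3.1.1 adds: "At laparoscopy biopsies of the peritoneum will be done and used later to confirm status of peritoneal disease", and describes these biopsies as belonging to the study and not to the staging procedure.

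**The concern.** The late-capture rule is built for drug trials, where the last dose marks the end of exposure and late harm is mostly foreseeable drug toxicity. Here the experimental treatment is a major operation. Its complications can appear or worsen after 30 days, and the important ones are foreseen in the protocol itself. Requiring an event to be unexpected therefore filters out the harms that the surgical arm is most likely to produce.

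The patients reached by the rule are those for whom surgery was not followed by chemotherapy, including those with the slowest recovery. If the DSMB tables and the final risk-benefit account are drawn from C3D, they would omit some of the late morbidity in this group. Section 3.2 keeps details of perioperative management off the case report forms, so there is no evident fallback in the database. Complications of a protocol procedure carried out before randomization would be missing as well.

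**Working it through.** The plan gives no figure to reproduce. The check sets the sections side by side and adds day counts.

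**Inputs.** 30 days (7.1.1, 7.2.1); usual start of chemotherapy 6–8 weeks after surgery = 42–56 days (3.5.1); recovery limit 16 weeks = 112 days, or 24 weeks = 168 days with thoracotomy (3.1.2).

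**1. Patient recovering, chemotherapy still planned.** Section 3.9 counts follow-up visits from completion of chemotherapy, so this patient is not in follow-up and surgery is not the last treatment. Section 7.3.3 applies, and a grade 3 or higher event is entered whether expected or not. Gap for such events: 0 days.

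**2. Patient removed as unrecovered at 16 weeks.** Surgery, with CHPP if given, is now the last treatment, and more than 30 days have passed. If the status is applied only on removal, the narrowed rule starts at day 112. If it is applied back to the operation, it starts at day 31. The two readings differ by 112 − 30 = 82 days; with the thoracotomy limit, 168 − 30 = 138 days. These figures measure the ambiguity in the text, not lost events. After removal both readings give the narrowed rule.

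**3. Patient removed at operation as not debulkable, or withdrawn soon after surgery.** The operation is the last treatment from the outset or from withdrawal, so the 7.2.1 condition is met from day 31, or from withdrawal if that is later. If no CHPP was given, there has been no dose of study drug and the 7.1.1 clock has no starting date.

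**4. Applying the late rule to one event.** Take a serious, related enterocutaneous fistula that arises after the rule has narrowed:

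| Destination | Condition | Met? |
|---|---|---|
| C3D (7.2.1) | serious, related and unexpected | No, if consistent with 6.2 |
| DSMB comparison (5.4) | at least possibly attributed | Yes |
| Continuing review (7.4.2) | serious, any attribution | Yes |

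The database condition is stricter than that of the safety comparison.

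**5. Which arm.** SA patients normally start chemotherapy within 14 days of randomization (2.3), so the case is mainly a GYMS one. Section 3.1.2 also allows SA patients a palliative gastrectomy. One who then never starts chemotherapy is in the same position.

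**6. Laparoscopy.** The order is laparoscopy, washings result, randomization (2.2.3, 3.1.1). Since 7.2.1 begins at randomization, events from the laparoscopy and study biopsies fall before capture opens, in both arms equally.

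**The case against.** The strongest reply is that 7.3.3 is the specific rule for post-operative recovery and keeps grade 3 or higher events. This stands for patients awaiting chemotherapy. A reader might infer that every GYMS patient has a gap between day 31 and the first cycle, of 42 − 30 = 12 to 56 − 30 = 26 days at the usual timing. The documents do not support that, because such a patient is not yet in follow-up. The reply does not settle the case of a patient already off treatment: 7.3.3 has no end date, and nothing says that it prevails once the 7.2.1 condition is met.

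Second, the events are not lost. They remain in source documents, and 7.4.2 sends related grade 3–4, all grade 5 and all serious events to the IRB. Deaths not due to progression are expedited under 7.4.1, and every death counts toward the primary endpoint. This stands: the defect is absence from C3D.

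Third, foreseen harms are not always expected in the regulatory sense. Section 7.1.3 also treats an event as unexpected if it exceeds the listed specificity or severity, and 6.2 gives no grades. Some late complications would pass the test, but the outcome would turn on individual judgement.

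Fourth, a between-arm bias is not shown. During chemotherapy, 7.3.4 drops package-insert grade 3 events that need no hospitalization, while 7.3.3 keeps all grade 3 events after discharge. The net direction across arms is therefore not established. The laparoscopy gap precedes allocation and cannot bias the comparison.

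Finally, 7.4.2 governs IRB reporting and 7.2.1 database entry. They differ in scope without strictly contradicting each other.

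**Conclusion.** The point holds for a defined subgroup: patients whose operation proves to be their last treatment. For them the narrowed rule applies from day 31, or from removal at the latest. Later complications of the kinds listed in 6.2 that are serious and related but expected then stay out of C3D. The two 30-day anchors differ, and neither is defined for these patients. The laparoscopy gap is a second, separate omission affecting both arms.

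The size cannot be computed. The documents give neither the proportion of operated patients who never start chemotherapy nor the rate of late surgical complications. A reader might take 30/112 = 27% or 30/168 = 18% as the share of surgical harm captured, but these are ratios of durations and say nothing about events. Nor do the documents support saying that the loss occurs only in GYMS or that the DSMB comparison necessarily understates surgical morbidity.

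The conclusion assumes that the DSMB tables come from C3D, which 5.1 names as the data collection system, and that the harms in 6.2 count as expected at the severity seen. It does not touch the primary survival analysis. It is a defect in a stated rule that is cheap to correct.

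**What to change.** - **One anchor.** Use the same starting point in 7.1.1 and 7.2.1, and define it for patients who have surgery but no chemotherapy, with or without CHPP.
- **End of the recovery phase.** State that 7.3.3 governs from discharge until the first systemic cycle or, for patients who never start chemotherapy, until the end of the recovery window in 3.1.2. That window must first be reconciled with 3.5.1, which gives about 6–8 weeks and then removes patients not recovered in the stated time. The 24-week limit also needs reconciling: 3.1.2 counts it from initial surgery and 3.2.8 from randomization.
- **Late rule.** Replace the three-part condition in 7.2.1 with serious and at least possibly related. This matches the attribution standard in 5.4. It remains narrower than 7.4.2, which ignores attribution; that is acceptable if IRB reporting stays a separate stream.
- **Start of capture.** Enter procedure-related events in C3D from the staging laparoscopy onward, in both arms.

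The cost is protocol wording, revised case report form instructions and modest extra data entry. No new visits or procedures are needed.

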7.3.2. During hospitalization for surgical resection

- Grade 2 events
- Grade 3 and 4 events which resolve during the first 72 hours following surgery

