Data will be collected using the NCI C3D web based data collection system. Quality of life will be assessed using questionnaires as specified in section 3.11.

5.2. **Response Criteria**

5.2.1. **Surgery + chemotherapy arm**

Because of the nature of peritoneal imaging and because cytoreductive surgery will likely eliminate all imageable disease, response can only be measured in terms of radiographic or symptomatic disease-free survival and overall survival. Patients will be followed with CT scans at predetermined intervals as described in Section 3.9. At any time point when there is evidence of progressive disease (imageable tumor nodules or increasing ascites persistent on CT scans as interpreted by the official interpretation of the imaging studies) the patients will be scored as progressive disease. In some cases this may require successive scans, but the time of recurrence will be retrospectively defined at the point the first scan demonstrated imageable disease. Patients who have symptoms of peritoneal tumor recurrence will be followed closely with serial scans and where necessary, laparoscopy (GYMS arm) in order to confirm disease status.

5.2.2. **Systemic chemotherapy alone arm**

Lesions will be evaluated using the RECIST criteria as described below.

Evaluation of target lesions*

- Complete Response (CR): Disappearance of all target lesions
- Partial Response (PR): At least a 30% decrease in the sum of the longest diameter (LD) of target lesions taking as reference the baseline sum LD.
- Progression (PD): At least a 20% increase in the sum of LD of target lesions taking as reference the smallest sum LD recorded since the treatment started or the appearance of one or more new lesions.
- Stable Disease (SD): Neither sufficient shrinkage to qualify for PR nor sufficient increase to qualify for PD taking as references the smallest sum LD.

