The study will be monitored by the NCI/CCR Data Safety and Monitoring Board on an annual basis to evaluate the safety of the two arms. The SAEs (typically grade 3 toxicities, or greater) will be reported according to type of toxicity, and maximal grade noted per patient, for toxicities with at least a possible attribution to the therapy provided on that arm. Comparisons will be made between the two arms using Cochran-Armitage tests for trend, or other appropriate methods, to determine if there is increased toxicity associated with either arm.

In addition, at the first Data Safety and Monitoring Board (DSMB) meeting held following the point at which half of the required total subjects have been enrolled (68 total), a single evaluation for futility will be undertaken. Evaluations for better than expected efficacy will also be made annually, beginning after half the subjects have been enrolled.

The futility evaluation will be performed as follows: based on the full data available at the time, a conditional power analysis will be performed to determine if the trial is unlikely to find an effect at the 0.05 two-tailed significance level with continued accrual based on an overall survival endpoint. Median survivals of 12 and 20 months correspond to 12-month survivals of 50% and 66% respectively. Using these as the values under the alternative, and using the actual proportions alive at 12 months, based on the observed fractions and the expected sample sizes at 12 months, the conditional power of the trial will be determined assuming accrual of the remaining patients to achieve a total of 136 patients. If the conditional probability of finding a difference at the two-sided 0.05 level at the conclusion of the trial is less than 20%, then it will be reasonable to recommend that no further patients will be enrolled.

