7.3.4. During systemic chemotherapy administration

- Grade 1 and 2 events that are listed in the package insert of any of the agents
- Grade 3 events that are listed in the package insert of any of the agents and do NOT require hospitalization. Events that initiate dose reduction will be captured as described in Section 7.1.1

Note: Events that result in a hospitalization for convenience will not be reported.

7.3.5. Concomitant medications:

Only those medications that the patient is taking at baseline on a routine basis or medications that cause an AE will be captured in C3D. {Thus onetime medications, PRN medications, and medications given to treat adverse events will not be captured in C3D.}

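### Grade 3-4 events that resolve within 72 hours of resection stay out of C3D, so the between-arm toxicity comparison would, by inference, lose perioperative events mainly from the GYMS arm

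*Combined protocol and SAP*

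**What the plan says.** Section 5.1 (Data Collection) names one system for clinical data: "Data will be collected using the NCI C3D web based data collection system". Quality of life is collected by questionnaire. Section 7.2.1 sets a broad capture rule: "Following randomization, all adverse events will be described in the source documents, reviewed by the designated research nurse, and captured in C3D".

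Section 7.3 then makes exceptions: "The following Adverse Events will be captured only in the source documents and will not be reported in C3D". Two of them reach grade 3 or above:

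- Section 7.3.2, for the surgical stay: "Grade 3 and 4 events which resolve during the first 72 hours following surgery".
- Section 7.3.4, for the chemotherapy phase: "Grade 3 events that are listed in the package insert of any of the agents and do NOT require hospitalization". Events that lead to a dose reduction are still captured.

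Section 5.4 describes the annual DSMB safety review. It reports "The SAEs (typically grade 3 toxicities, or greater") by type of toxicity and by each patient's maximal grade, limited to events at least possibly attributed to that arm's therapy. It continues: "Comparisons will be made between the two arms using Cochran-Armitage tests for trend, or other appropriate methods". No significance level is given for this test.

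Section 7.4.2 has the principal investigator report to the IRB at continuing review "All Grade 3 and 4 events that are possibly, probably or definitely related to the research", with no 72-hour exemption.

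**The concern.** The comparison in Section 5.4 is meant to show whether either arm carries more toxicity. The events removed by Section 7.3.2 fall in the severity range it compares, and they arise around an operation that one arm has by design and the other only when palliation is indicated. A grade 4 event that threatened life and was controlled within three days would not be in the database. Section 7.3 has no clause that returns serious events to C3D.

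The timing adds weight. Under Section 5.5, toxicity and adverse events are all that the DSMB examines until 68 patients have been randomised. Section 1.2 also says the safety of the combined-modality treatment will be monitored. A safety comparison that loses perioperative events mainly from the arm with the added surgery and heated intraperitoneal chemotherapy is weakest where it is most needed.

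**Working it through.** The plan states no figure to reproduce. The check is a reading of the sections together, followed by an illustration of size.

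**1. What is left out.** Sections 7.3 and 7.3.2 send grade 3 and 4 events of the surgical stay to source documents only, if they resolve within 72 hours of surgery. Grade 5 events are not listed, so they are captured. So are grade 3-4 events of the surgical stay that last beyond 72 hours.

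**2. Whom it affects.** Section 3 plans gastrectomy and/or metastasectomy for all GYMS patients. Sections 3 and 3.1.2 allow SA patients palliative gastrectomy, which includes tumour resection, so their surgical stay comes under the same rule. The protocol gives no expected number of these operations. The attribution limit in Section 5.4 might also remove SA surgical events from the comparison, but the text does not say so.

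**3. Whether the comparison uses C3D.** Sections 5.4 and 5.5 do not name their data source. Section 5.1 names C3D and no other clinical system. The events could not readily be reconstructed from other entries: Section 3.2 keeps perioperative management details off the CRFs, and Section 7.3.5 leaves out medications given to treat adverse events. That C3D feeds the comparison is therefore a strong inference, not a stated fact.

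**4. When the analysed value changes.** A patient's maximal grade for a toxicity type changes only if no captured event of that type has an equal or higher grade.

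**5. The second exclusion.** Section 7.3.4 applies in both arms. It may weigh more on SA, where chemotherapy starts within 14 days of randomisation (Section 3.5.1) and responders may go beyond 12 cycles (Section 3.5.2), while GYMS patients who do not recover in time leave treatment (Section 3.1.2).

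**6. Illustration.** The documents give no adverse event rates by arm. All rates below are assumed, as is a two-sided 0.05 level. The endpoint is simplified to any grade 3+ event, yes or no, in place of the trend test by toxicity type. With n per arm and rates p1 and p2:

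- d = |p1 − p2|, p̄ = (p1 + p2)/2
- SE0 = √[2p̄(1 − p̄)/n], SE1 = √{[p1(1 − p1) + p2(1 − p2)]/n}
- power = Φ[(d − 1.96·SE0)/SE1]

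Example with 0.65 versus 0.40 and n = 68: SE0 = √(2 × 0.525 × 0.475/68) = 0.0856; SE1 = √[(0.2275 + 0.24)/68] = 0.0829; power = Φ[(0.25 − 0.1679)/0.0829] = Φ(0.99) = 84%.

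The recorded rate is the true rate × (1 − share of affected patients whose only grade 3+ events are excluded).

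| Hidden in GYMS | Hidden in SA | Recorded GYMS vs SA | Power, 68 per arm |
|---|---|---|---|
| 0 | 0 | 65% vs 40% | 84% |
| 10% | 0 | 58.5% vs 40% | 58% |
| 20% | 0 | 52% vs 40% | 29% |
| 25% | 0 | 48.75% vs 40% | 17% |
| 10% | 25% | 58.5% vs 30% | 93% |
| 25% | 40% | 48.75% vs 24% | 86% |

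At 34 per arm, about the size when 68 patients have been randomised, the first, second and fourth rows give 54%, 33% and 11%.

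Rows 2 to 4 show the effect of Section 7.3.2 alone. The last two rows add losses in SA under Section 7.3.4, and power is then at or above the full-capture value. The result depends on shares that no document supplies.

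**The case against.** The strongest reply is that the net bias is not shown. A reader might infer that these rules hide toxicity in the surgical arm only and so make surgery look safer. The documents do not support that. SA patients who have palliative gastrectomy come under Section 7.3.2, and Section 7.3.4 removes grade 3 events in both arms, possibly more in SA. The last two rows of the table show that the two exclusions can offset each other. This part of the reply stands.

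The window is also narrow. Deaths and longer-lasting events remain, and a captured event of the same type and equal or higher grade leaves the maximal grade unchanged. Nothing shows that 10% or 25% of affected patients would have only excluded events. This stands too, and it limits any claim about size.

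It can also be said that the events are not lost: they stay in source documents, related grade 3-4 events and all serious events go to the IRB under Section 7.4.2, and the principal investigator reviews toxicities quarterly under Section 5.5. That is true, but none of these routes is described as feeding the between-arm test. Nor does the possibility of offsetting losses make the comparison sound: two unmeasured omissions that may cancel still leave a result that cannot be interpreted.

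Finally, short-lived events after major surgery are expected, and a sponsor may reasonably want a table without them. A flag allows that; leaving them out of the database removes the choice.

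**Conclusion.** The point holds in a limited form. Followed as written, Section 7.3.2 removes short-lived grade 3-4 perioperative events from C3D, predominantly in GYMS, and has no exception for serious events. If the comparison in Section 5.4 is drawn from C3D, which is inferred from Section 5.1, it understates perioperative toxicity mainly in the surgical arm.

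The further conclusion that the overall comparison favours GYMS does not follow, because Section 7.3.4 removes events in both arms and the documents give no rates for either exclusion. The power figures rest on assumed rates, an assumed 0.05 level and a binary simplification, and should not be quoted as an estimate of the trial's loss. The omission should be corrected because it falls unevenly on the arms in a safety comparison, cannot be quantified afterwards from the database, and is inexpensive to avoid.

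**What to change.** - Enter in C3D, for both arms, every grade 3-5 event at least possibly related to assigned treatment, including those now excluded by Sections 7.3.2 and 7.3.4. Add a flag for events resolved within 72 hours of surgery.
- State in Section 5.4 that the DSMB comparison uses this set, tabulated with and without flagged events.
- In Section 5.4, replace the SAE wording with grade 3 or higher adverse events. Seriousness, as defined in Section 7.1.4, is a different concept from severity grade.
- At the same time, reconcile Section 7.1.1, which requires all adverse events on the CRF subject to exceptions in Section 6.1, with Section 7.3. Section 6.1 lists no such exceptions.

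The cost is some extra data entry. It is limited because Section 7.4.2 already obliges the principal investigator to compile all related grade 3 and 4 events and all grade 5 events. Treatment and visits are unaffected.
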